## **8.8 Efficacy Evaluation**

### **8.8.1 *Analysis of Efficacy***

The primary objective of this study is to assess safety, not efficacy. However, IGA and percent BSA treated and affected with disease will be assessed to document any changes that are observed with regard to IGA and percent BSA. Frequency distributions of the observed and change from Baseline IGA severity scores will be presented for each visit for the Evaluable population.

Descriptive statistics will be provided for observed and changes from Baseline with respect to both the percent BSA affected and to be treated for the Evaluable and PK populations.

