14.2 Subject Discontinuation

A subject may be withdrawn from the study prior to completion for any of the following reasons:

- Whenever the subject and/or parent/guardian decide it is in the subject's best interest to withdraw. NOTE: if the subject and/or parent/guardian decide it is in the subject's best interest to withdraw due to an AE then it should be classified as withdrawal due to an AE.
- Whenever the investigator decides it is in the subject's best interest to be withdrawn
- AEs
- Worsening of condition or treatment failure (in the opinion of the investigator)
- Intercurrent illness which may, in the investigator's opinion, significantly affect assessment of clinical status

- Noncompliance
- Pregnancy
- Lost to follow-up
- Sponsor administrative reasons

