18.3 Statistical Methods

All statistical analyses and summaries will be prepared using SAS[®] unless otherwise stated. All subjects enrolled in the study who were dispensed and applied test article at least once will be included in the analysis of safety and will be considered the Safety population. Subjects will apply the initial dose of test article in the clinic on Day 1. All enrolled subjects who applied at least one dose of test article and returned for at least one post-baseline visit will be included in the modified ITT (mITT) population. Subjects discontinued from the study at Visit 2 due to abnormal screening laboratory test results or other ineligibility criteria (screen failures) will be excluded from the HPA axis suppression summaries. Subjects included in the pharmacokinetic analysis (PK population) must not have any significant protocol deviations and must have at least an 80% - 120% dose compliance based on number of applications. Clinical study sites should make every effort so that subjects do not miss consecutive doses.

Demographic and baseline characteristics (including the percent BSA affected and the percent BSA treated) will be summarized for the mITT, Safety and PK populations. In addition, demographic variables, AEs and primary reason for screen failure will be summarized separately for screen fail subjects. Frequency counts and percentages will be reported for categorical data and sample size, mean, SD, median, minimum and maximum will be reported for the continuous variables.

Frequency counts and percentages for IGA scores at each visit and descriptive statistics (sample size, mean, SD, median, minimum and maximum) will be summarized for the percent BSA affected and the percent BSA treated with the test article at each visit.

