#### 8.2.2 *Evaluable Population*

The Evaluable population will include those subjects in the Safety population who have both Screening and EOS serum cortisol data (pre- and post-cosyntropin stimulation) and meet the following criteria:

- Meets all inclusion/exclusion criteria, including normal response to cosyntropin stimulation defined as a Screening CST with a 30-minute post-stimulation cortisol level  $>18 \mu\text{g/dL}$ .
- Screening and EOS CST were conducted between 7-9 AM.
- EOS CST was conducted within  $\pm 1$  hour of the Screening CST.
- Applied at least 80% and no more than 120% of the expected number of applications and applied the final dose no more than 14 hours prior to the start of the CST test.

- Has not taken or applied any medications that may interfere with HPA axis function.
- Do not have any other significant protocol deviations.

HPA axis suppression analysis will be conducted on the Evaluable and Safety populations.

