## **9. CHANGES TO PROTOCOL**

The protocol defined the Safety, modified Intent-to-Treat (mITT), and PK populations. Since an efficacy analysis is not the primary endpoint for this protocol, the mITT population has been replaced with the Evaluable population to be used for the analysis of HPA suppression response. Requirements for inclusion in the Evaluable population are specified so that the CST are consistent between the subjects.

The protocol included the determination of the approximate amount of test article applied per cm^2 prior to the collection of the PK samples at Visit 3 from the estimate of the percent BSA treated with the test article and the amount of test article applied based on the before and after weights of the dose prior to the blood draws. This data was not captured for this study, therefore, this determination will not be performed.

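### Post-Baseline IGA and percent BSA are tabulated only in CST- and compliance-defined populations (SAP 8.8.1), which drop uncleared subjects who stop early and keep Day 8 clearers

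*SAP*

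**What the plan says.** **Which tables use which population.** SAP 8.8.1 on IGA: "Frequency distributions of the observed and change from Baseline IGA severity scores will be presented for each visit for the Evaluable population". On BSA: "Descriptive statistics will be provided for observed and changes from Baseline with respect to both the percent BSA affected and to be treated". These BSA summaries are limited to two sets, Evaluable and PK. No post-Baseline efficacy table uses the Safety population. Screening and Baseline IGA, by contrast, are tabulated for Safety as well as Evaluable and PK (SAP 8.6.5).

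**How the populations are defined.** Evaluable (SAP 8.2.2) requires complete Screening and EOS cortisol data and, among other conditions:
- "Screening and EOS CST were conducted between 7-9 AM";
- an EOS CST within one hour of the Screening clock time;
- a last dose no more than 14 hours before the CST;
- no medication that may interfere with the HPA axis;
- "Applied at least 80% and no more than 120% of the expected number of applications";
- no other significant deviation.

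The PK population (SAP 8.2.3) has the same 80% to 120% rule and excludes significant deviations, but sets no CST condition.

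**Expected doses.** SAP 8.7 sets 14 for subjects who are clear at Day 8 and leave, and 28 for those who go on to Day 15 or terminate early.

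**Why mITT was dropped.** Protocol 18.3 defined mITT as "All enrolled subjects who applied at least one dose of test article and returned for at least one post-baseline visit". SAP 9 notes that efficacy is not the primary endpoint and says that "the mITT population has been replaced with the Evaluable population to be used for the analysis of HPA suppression response", with criteria chosen so that the CSTs are consistent between subjects.

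**The concern.** A population designed to make cortisol tests comparable is being used for plaque severity. The hour of a CST has no bearing on IGA or BSA, and SAP 9 gives no reason tied to those outcomes beyond saying that efficacy is not primary. The HPA endpoint, for which Evaluable was built, is reported in both Evaluable and Safety (SAP 8.2.2, 8.9.3). IGA and BSA get no Safety table.

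Membership also depends partly on outcome, because the expected number of doses depends on whether the subject has cleared. Protocol 14.2 lists worsening and treatment failure among the reasons for withdrawal, and Protocol 6.2.1 provides for discontinuation if disease becomes unmanageable within the weekly limit. Such subjects can have usable data: IGA and percent BSA affected are scheduled for everyone at Day 8 and again at the early-termination visit. Protocol 18.2.1 promises descriptive statistics for changes in IGA and BSA, and these tables would leave that part of the collected data out.

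**Working it through.** **1. The plan's dose counts.** Twice-daily dosing from Day 1 to the evening of Day 14 gives 2 × 14 = 28. Dosing to the evening of Day 7 gives 2 × 7 = 14. Both figures in SAP 8.7 are reproduced.

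**2. The 80% to 120% rule.** On 28 doses, the minimum is 0.80 × 28 = 22.4, so 23 applications. On 14 doses, the minimum is 0.80 × 14 = 11.2, so 12, and the maximum is 1.20 × 14 = 16.8, so 16.

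**3. Who passes, with no missed doses.**

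| Subject | Doses | Expected | Compliance | Passes dose rule |
|---|---|---|---|---|
| Clear at Day 8, exits that day | 14 | 14 | 100% | yes |
| Not clear, stops after Day 7 evening | 14 | 28 | 50.0% | no |
| Not clear, stops after Day 11 evening | 22 | 28 | 78.6% | no |
| Not clear, stops after Day 12 evening | 24 | 28 | 85.7% | yes |
| Clear at a Visit 3 held on Day 9, EOS next day | 18 | 14 | 128.6% | no |

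Rows 1 and 2 show the asymmetry: the same 14 doses keep the clearer and remove the non-clearer. Failing the dose rule removes a subject from Evaluable and PK alike, and so from every post-Baseline IGA and BSA table. In row 4 the CST falls on Day 13, the first day of the Day 15 ± 2 window. Row 5 is a clearer who is lost as over-compliant, so the rule does not work in one direction only.

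**4. Possible size.** Protocol 18.1 plans at least 20 evaluable subjects from about 25 enrolled, which leaves 25 − 20 = 5 others. The SAP defines no responder, so the counts below are assumptions. Let 10 of 20 Evaluable subjects respond (50%).
- None of the 5 responds: 10/25 = 40%.
- All 5 respond: 15/25 = 60%.
- One excluded non-responder: 10/21 = 47.6%, so the Evaluable figure is 2.4 points too high. With five it is 50% − 40% = 10 points too high.
- For other Evaluable rates the same bounds are 6/25 to 11/25 (24% to 44%) at 30%, and 14/25 to 19/25 (56% to 76%) at 70%.

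**5. An effect in the opposite direction.** Day 8 clearers leave the study, and SAP 8.8.2.1 uses observed data without imputation, so they are missing from the Day 15 column. If c of the 10 responders cleared at Day 8, Day 15 shows (10 − c)/(20 − c): 9/19 = 47.4% for c = 1, and 5/15 = 33.3% for c = 5.

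**The case against.** The strongest reply is that nothing of consequence rests on these tables. Both documents say that the study assesses safety. There is no responder definition, test or comparator. SAP 8.1 generally supports tables with subject listings, and SAP 8.5 tabulates reasons for withdrawal for all enrolled subjects, so a withdrawal for worsening is not hidden. SAP 9 discloses the change of population, and the protocol never assigned post-Baseline IGA or BSA to mITT, so no protocol-specified efficacy population was abandoned. All of this stands and keeps the point minor. It does not repair the tables, since a listing or a disposition row does not change a table's denominator.

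A reader might also infer more than the documents support:
- *That treatment failures as a class are missing.* They are not. Evaluable has no response criterion, and a subject who fails to improve but doses to about Day 12 or later, with a valid CST and no other exclusion, stays in.
- *That anyone whose last visit is by Day 12 is out.* Day 8 clearers are judged against 14 doses and can be Evaluable.
- *That a late CST removes a subject from every table.* PK has no clock-time criterion, so percent BSA is lost only if the lateness is rated a significant deviation. Sites are also told to reschedule to the next day when the timing conditions are not met (Protocol 13.1, SAP 7.1).

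**Conclusion.** The point holds as a minor one. Post-Baseline IGA and percent BSA appear only in populations not built for them, and the 14- versus 28-dose rule excludes uncleared subjects with fewer than 23 applications while a Day 8 clearer with 14 can stay. That part follows directly from SAP 8.2.2, 8.2.3, 8.7 and 8.8.1.

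It is tempting to conclude that the tables will overstate benefit. The documents support only that they may. CST-timing exclusions have no evident link to response, and the absence of Day 8 clearers from the Day 15 column can lower the apparent response. The 40% to 60% range around an Evaluable rate of 50% rests on assumed counts (10 of 20 responders, 5 other treated subjects) and bounds what is possible; it is not an estimate.

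**What to change.** In SAP 8.8.1, also present observed and change-from-Baseline IGA and percent BSA for Safety subjects with at least one post-Baseline assessment, in substance the protocol's mITT set. Include early-termination values. Add an EOS row, defined as the last on-study assessment, that includes subjects who cleared and left at Day 8 or 9. For percent BSA affected, the Day 8 value would serve for those who leave on Day 9, since none is scheduled that day. Percent BSA to be treated is recorded only at Baseline and Day 8, so the EOS row applies to IGA and percent BSA affected. Keep the Evaluable and PK tables as supportive.

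The cost is a short change of SAP wording and one extra set of tables run on another population flag, with no new data collection. The figures may look slightly less favourable.

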### **8.8.2 *Statistical / Analytical Issues***

#### **8.8.2.1 Handling of Dropouts or Missing Data**

All summaries will be based on observed data only. Imputation of missing clinical data values will not be performed. For the PK analyses, concentrations reported as below the lower limit of quantitation will be imputed as zero.

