5.1.2 Exclusion Criteria

1. Subject has spontaneously improving or rapidly deteriorating plaque psoriasis.
2. Subject has guttate, pustular, erythrodermic or other non-plaque forms of psoriasis.
3. Subject has a physical condition which, in the investigator's opinion, might impair evaluation of plaque psoriasis, adrenal axis function (e.g., Addison's Disease, Cushing's Syndrome) or which exposes the subject to an unacceptable risk by study participation.
4. Subject has used any phototherapy (including laser), photo-chemotherapy or systemic psoriasis therapy including methotrexate, retinoids, cyclosporine or biologics within 30 days prior to the initiation of treatment with the test article.
5. Subject has used systemic corticosteroids (including oral or intramuscular) or topical, inhaled or intranasal corticosteroids within 30 or 14 days, respectively, prior to Part B of the Screening Visit and/or the subject has used systemic or topical corticosteroids between Part B of the Screening Visit and the initiation of treatment.
6. Subject has had prolonged exposure to natural or artificial sources of ultraviolet radiation within 30 days prior to the initiation of treatment or is intending to have such

⁶ Effective forms of birth control include hormonal contraceptives [oral, injectable, transdermal or intravaginal] or intrauterine device (IUD) for two cycles (e.g., eight weeks) prior to test article application, condom and spermicidal or diaphragm and spermicidal). Other acceptable forms of birth control include: a) abstinence for subjects who are not sexually active or b) if the subject is in a monogamous relationship with a partner who is sterile (e.g., vasectomy performed at least six months prior to the subject's initiation of treatment). Subjects who become sexually active or begin to have relations with a partner who is not sterile during the trial must agree to use an effective form of birth control for the duration of the study.

exposure during the study that is thought by the investigator to likely modify the subject's disease.

7. Subject has used topical psoriatic therapy including tar, anthralin, retinoids, vitamin D analogs (e.g., Dovonex[®]) within 14 days prior to the initiation of treatment with the test article.
8. Subject has used emollients/moisturizers on areas to be treated within one day prior to the initiation of treatment with the test article.
9. Subject is currently using lithium or Plaquenil (hydroxychloroquine).

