18. STATISTICAL CONSIDERATIONS

18.1 Sample Size

Subject enrollment will continue until at least 20 subjects with both Screening and EOS serum cortisol data (pre- and post-cosyntropin stimulation) have completed the study without any significant protocol deviations (evaluable subjects). This may require the enrollment of approximately 25 subjects.

No formal power calculations were performed to establish the sample size. The number of subjects enrolled who complete the study is historically consistent with other HPA studies.

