## **7.2 Pharmacokinetic Tests**

Blood for PK analysis will be drawn three times: at Screening (pre-application, time=0), Day 8, and Day 15 (unless IGA=0 at Day 8), approximately 12 hours after the dose on the previous day. All eligible subjects will have blood drawn at Screening for baseline drug concentration in plasma. On Day 8, all subjects, regardless of lesion clearance, will have blood drawn for assessment of trough drug concentration in plasma. At the Day 15 visit, subjects who have continued to treat lesions will have a final PK blood sample collected approximately 12 hours after their Day 14 evening application and just prior to the initiation of the CST.

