#### **8.8.2.3 Multicenter Studies**

Data tabulations will be per study site, as well as, overall.

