#### ***8.9.4 Pharmacokinetic Analyses***

Morning trough concentrations of HBP in plasma at Screening, Day 8 and Day 15 will be summarized for the PK population using geometric mean, coefficient of variation in addition to n, mean, median, standard deviation, minimum and maximum.

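### Setting BLQ concentrations to zero makes the geometric mean required by the SAP zero or undefined at any visit with a BLQ sample, as is expected at Screening

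*SAP*

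**What the plan says.** SAP 8.8.2.1 (Handling of Dropouts or Missing Data) sets one rule, without exception: "For the PK analyses, concentrations reported as below the lower limit of quantitation will be imputed as zero". SAP 8.9.4 (Pharmacokinetic Analyses) names the visits, "Morning trough concentrations of HBP in plasma at Screening, Day 8 and Day 15", and the statistics: the concentrations "will be summarized for the PK population using geometric mean, coefficient of variation in addition to n, mean, median, standard deviation, minimum and maximum".

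SAP 7.2 describes the sampling: "Blood for PK analysis will be drawn three times: at Screening (pre-application, time=0), Day 8, and Day 15". The first sample therefore precedes any test article. Under Protocol 5.1.2 it also follows a corticosteroid washout, counted back from Part B of Screening: 30 days for systemic products and 14 days for topical, inhaled or intranasal ones. SAP 8.8.2.3 adds that "Data tabulations will be per study site, as well as, overall".

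Neither document has a separate BLQ rule for log-scale statistics, and SAP Section 9 (Changes to Protocol) does not mention the matter.

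**The concern.** A geometric mean needs strictly positive values. The SAP puts zeros into the data and then asks for a geometric mean of them. A geometric CV would fail in the same way, and the SAP does not say whether its coefficient of variation is arithmetic or geometric.

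PK properties are one of the two aims in the study objective, and trough concentration is the only PK measure. Followed exactly, the plan prints a geometric mean that says nothing about exposure at any affected visit. The less visible risk is that zeros are dropped in programming. The geometric mean would then describe quantifiable samples only, on a different n from the arithmetic mean in the same table, and would be too high.

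**Working it through.** The plan has no figure of its own to reproduce. The first two steps are algebra. The last three need assumptions, because the documents give no lower limit of quantitation (LLOQ), BLQ rate or variance.

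**1. Effect of one zero.** The geometric mean is (x₁·x₂·…·xₙ)^(1/n) = exp(mean of ln xᵢ). If any xᵢ = 0, the product is 0 and ln xᵢ does not exist. In an illustrative lognormal sample of 20 (arbitrary units, median 100, log-SD 0.8), the geometric mean was 103.0. Setting one value to zero made it 0, and so did 5, 10 or 20 zeros.

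**2. Screening.** The sample is pre-dose and after washout, so most or all values should be BLQ. Halobetasol is already marketed (Protocol Section 1), so residual drug in a few subjects cannot be excluded, but one BLQ value is enough. If all values are BLQ, the arithmetic mean and SD are both 0 and the arithmetic CV is 0/0.

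**3. Chance of at least one zero at a visit.** P = 1 − (1 − f)ⁿ, with f the BLQ probability per sample and samples independent. I take n = 20 and n = 25 from the evaluable target and approximate enrollment in Protocol 18.1. The PK population has no stated size, so both are assumptions. Example: 1 − 0.95²⁰ = 1 − 0.3585 = 64%.

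| BLQ rate f | n = 20 | n = 25 |
|---|---|---|
| 1% | 18% | 22% |
| 5% | 64% | 72% |
| 10% | 88% | 93% |
| 20% | 99% | 99.6% |

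**4. Size of the error under alternative rules.** Assume log-concentration ~ N(0, s²), so that the true geometric mean is 1, with s² = ln(1 + CV²), z = Φ⁻¹(f) and LLOQ = exp(sz). Ratios to the truth are:

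- zeros dropped, geometric mean: exp[s·φ(z)/(1 − f)]
- LLOQ/2 substituted, geometric mean: exp[f(sz − ln 2) + s·φ(z)]
- BLQ = 0, arithmetic mean: Φ(s − z)

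Example at CV 100% and f = 50%: s = √ln 2 = 0.8326, z = 0, φ(z) = 0.3989. Dropped: exp(0.8326 × 0.3989/0.5) = 1.94. LLOQ/2: exp(−0.3466 + 0.3321) = 0.99. Arithmetic: Φ(0.8326) = 0.80.

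| CV | f | Zeros dropped | LLOQ/2 | Arithmetic, BLQ = 0 |
|---|---|---|---|---|
| 50% | 10% | 1.10 | 0.95 | 0.96 |
| 50% | 30% | 1.26 | 0.89 | 0.84 |
| 50% | 50% | 1.46 | 0.85 | 0.68 |
| 100% | 10% | 1.18 | 0.97 | 0.98 |
| 100% | 30% | 1.51 | 0.95 | 0.91 |
| 100% | 50% | 1.94 | 0.99 | 0.80 |
| 150% | 10% | 1.24 | 0.98 | 0.99 |
| 150% | 30% | 1.72 | 1.00 | 0.95 |
| 150% | 50% | 2.38 | 1.09 | 0.86 |

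With zeros dropped, the geometric and arithmetic means in one table would err in opposite directions.

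**5. Censored lognormal maximum likelihood.** In simulation (2,000 samples of n = 20 per scenario, same grid), the average estimate was about 0.98 to 1.00 times the truth. This describes bias only. In a separate run of 1,000 samples at 50% BLQ, the 5th to 95th percentiles were 0.79 to 1.21 at CV 50% and 0.55 to 1.53 at CV 150%; much of that spread is ordinary sampling error.

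**The case against.** The strongest reply is that little depends on this statistic. The geometric mean is one of eight listed, and n, mean, median, SD, minimum and maximum remain calculable with BLQ = 0. No test, limit or decision rule uses it, and the protocol asks only that troughs be calculated and summarized. SAP 8.1 says that summary tables will generally be supported by subject listings and allows modifications for unanticipated data features. All of this stands and limits the harm, but BLQ values in a pre-dose sample are not unanticipated.

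Second, the visit where the failure is expected is the one where it matters least: a Screening geometric mean of zero misleads nobody. That is fair. For Day 8 and Day 15 the documents support only the statement that BLQ values may occur.

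Third, the overstatement figures describe dropped zeros, which the SAP does not instruct; read literally, the result is a conspicuous zero or blank. This is also right. Those figures show what an unstated programming choice could do, not what the plan says will happen.

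Fourth, LLOQ/2 and any reporting cut-off are conventions, and a censored-likelihood fit would be fragile in per-site tables (about 25 subjects over about four sites is roughly six each). Both points hold and shape the fix.

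None of them reconciles the two SAP rules.

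**Conclusion.** The point holds. Applied as written, SAP 8.8.2.1 and 8.9.4 give a zero or undefined geometric mean at every visit with a BLQ sample. That conclusion needs no distributional assumption. Its occurrence at Screening is a strong inference from the pre-dose timing and the washout; its frequency at Day 8 and Day 15 cannot be determined from the documents.

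If zeros were dropped instead, the overstatement would be 1.10 to 1.24 times at 10% BLQ and 1.46 to 2.38 times at 50%, for lognormal concentrations with a CV of 50% to 150%. The effect is confined to a descriptive PK table. It should still be corrected before analysis, because the table reports the study's only PK measure and the correction is cheap.

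**What to change.** Amend SAP 8.8.2.1 and 8.9.4 as follows:

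1. Keep BLQ = 0 for the arithmetic statistics only.
2. Report n (%) BLQ at each visit.
3. State whether the CV is arithmetic or geometric.
4. Compute the geometric mean, and the geometric CV if used, under one prespecified, footnoted non-zero rule. LLOQ/2 is workable in both overall and per-site tables; censored lognormal maximum likelihood is an alternative better kept to the overall table. Show these statistics as not calculated when more than half of the samples are BLQ.
5. At Screening, report only n (%) BLQ and the range.

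The cost is a few sentences and a table footnote, with no new data. The substitution value and the cut-off remain conventions. LLOQ/2 can be off by up to about 15% at 50% BLQ (CV 50% to 150%). Keeping BLQ = 0 biases the arithmetic mean low, by 4% at 10% BLQ and 32% at 50% BLQ if the CV is 50%, so n (%) BLQ should appear beside it.
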